4.7.1.6 Adjustment of Starting Dose in Special Populations

Renal impairment

Insufficient data are available to provide a dosage recommendation for ribociclib in patients with renal impairment.

Patients with baseline renal impairment are excluded from the study (serum creatinine > ULN or creatinine clearance <50 mL/min). Patients who experience renal impairment of grade 2 or higher during the treatment period should discontinue treatment and should be followed for safety assessments.

Elderly

Physicians should exercise caution in monitoring the effects of ribociclib in the elderly. Insufficient data are available to provide a dosage recommendation.

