3.0 PATIENT SELECTION

3.1 Inclusion Criteria

- 1. Patient has signed the Informed Consent (ICF) prior to any screening procedures being performed and is able to comply with protocol requirements.
- 2. Age \geq 18 years at time of study entry.
- 3. Willingness and ability to comply with study and follow-up procedures.
- 4. Histological confirmation of diagnosis of low-grade serous carcinoma of ovary, fallopian tube or peritoneum; Original diagnosis of de novo low-grade serous carcinoma or Original diagnosis of serous borderline tumor with subsequent diagnosis of low-grade serous carcinoma
 - In order to prevent inclusion of patients with high-grade serous carcinoma, diagnosis of low-grade serous carcinoma will be verified as part of a screening review by a gynecologic pathologist. Tissue for confirmation can be from primary tumor or recurrence.
- 5. Patient must have recurrent, measurable disease by RECIST v1.1.
- 6. There are no restrictions on number of prior therapies.
- 7. Patient cannot have previously received a prior cyclin dependent kinase inhibitor (CDKi). Patients who were treated with letrozole or another aromatase inhibitor for other indications must have not taken the drug for 6 months prior to initiating letrozole for this trial and may not have progressed on treatment.
- 8. Patients must not have remaining ovarian function to be included. In women who have at least one retained ovary, menopause must be confirmed with laboratory confirmation. Women who have ovarian function are eligible but must be placed on hormonal suppression. Menopause must be confirmed with laboratory confirmation, to include an estradiol level as this is assessed within 8 weeks of patient having been on tamoxifen.
- 9. Eastern Cooperative Oncology Group (ECOG) performance status (PS) 0-2
- 10. Resolution of all acute toxic effects of prior therapy or surgical procedures to National Cancer Institute (NCI) CTCAE Grade ≤ 1. Patients with grade 1 taxane-induced neuropathy, any grade alopecia, amenorrhea, or other toxicities not considered a safety risk for the patient as per investigator's discretion are eligible.

- 11. Patient has adequate bone marrow and organ function as defined by the following laboratory values at screening:
 - a. Absolute neutrophil count ≥1.5 × 10⁹/L
 - b. Platelets $\geq 100 \times 10^9/L$
 - c. Hemoglobin ≥9.0 g/dL

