 - d. Potassium, total calcium (corrected for serum albumin), magnesium, sodium and phosphorus within normal limits for the institution or corrected to within normal limits with supplements before first dose of study medication
 - e. INR ≤1.5 (unless patient is receiving permitted anticoagulants and the INR is within the therapeutic range of intended use for that anticoagulant within 7 days prior to the first dose of study drug).
 - f. Serum creatinine <1.5 mg/dL or creatinine clearance ≥50 mL/min
 - g. In the absence of liver metastases, alanine aminotransferase (ALT) and aspartate aminotransferase (AST) < $2.5 \times ULN$. If the patient has liver metastases, ALT and AST < $5 \times ULN$
 - h. Total bilirubin < ULN; or total bilirubin \le 3.0 x ULN or direct bilirubin \le 1.5 x ULN in patients with well-documented Gilbert's Syndrome.
- 12. Patient with available standard 12-lead ECG with the following parameters at screening:
 - a. QTcF interval at screening <450msec (using Fridericia's correction)
 - b. Resting heart rate 50-90bpm
- 13. Must be able to swallow ribociclib and letrozole capsules/tablets.
- 14. Patients receiving tamoxifen or toremifene must have washout period of 5 half-lives prior to randomization.

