4.1 TREATMENT PLAN: Ribociclib

Ribociclib will be supplied by Novartis or its designee in the form of 200 mg hard gelatin capsules or tablets as individual patient supply packaged in bottles. Storage conditions are described in the medication label.

All dosages prescribed and dispensed to the patient and all dose changes during the study must be recorded.

Ribociclib will be administered as a flat-fixed dose of 600 mg daily, and not by body weight or body surface area.

Patients must be instructed to return unused study drugs to the site at discontinuation or completion of treatment. The site personnel must ensure that the appropriate dose of each study drug is administered and that the drug accountability is performed.

Ribociclib must be taken as follows:

- Patients should be instructed to take the ribociclib capsules/tablets with a large glass of water (~250 ml) at the same time each day.
- Ribociclib can be taken without regard to meals; however dietary habits around the time of dosing should be as consistent as possible throughout the study
- Patients should be instructed to swallow the ribociclib capsules/tablets whole and not to chew, crush or open them.
- If vomiting occurs during the course of treatment, no re-dosing of the patient is allowed before the next scheduled dose
- Any doses that are missed (not taken within 6 hours of the intended time) should be skipped and should not be replaced or made up on a subsequent day.
- Patients must avoid consumption of grapefruit, grapefruit hybrids, pummelos, star-fruit, Seville oranges or products containing the juice of each during the entire study and preferably 7 days before the first dose of study medication, due to potential CYP3A4 interaction with the study medications. Orange juice is allowed.
- No herbal or dietary supplements are permitted, due to potential interactions with ribociclib; multivitamins are allowed.

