6.0 Study Parameters

6.1 Pre-Treatment Evaluations (Screening)

The following must be collected/ performed within 28 days prior to Cycle 1, day 1 of treatment. Clinical and laboratory evaluations performed as part of routine standard of care do not need to be repeated if performed within the appropriate window.

- Voluntary, written, dated, and signed informed consent must be obtained before any study specific procedures are performed (with the exception of certain imaging assessments if meeting the criteria defined in this section).
- Radiographic tumor assessments that were performed before the signing of the informed consent form as routine procedures (but within 28 days prior to study enrollment) do not need to be repeated and may be used as baseline assessments, as long as:
 - The tests were performed per the method requirements outlined in the Tumor Assessment Requirement Flowchart, the Efficacy Assessments sections.
 - Appropriate documentation indicating that these radiographic tumor assessments were performed as standard of care is available in the patient's source notes
- Complete medical history and disease treatment history.
- UPT in WOCBP
- ECOG PS
- Baseline AE assessment
- Physical exam with vital signs
- Labs: CMP, CPK, CBC with differential (diff), Uric acid, Urinalysis
- ECG
- Tumor assessment CT chest, abdomen, and pelvis, or MRI
- Concomitant medication
- CA-125
- Lipid panel (total cholesterol, HDL, LDL, triglycerides) fasting preferred
- Coagulation (PT and INR)
- Submission of an H&E stained slide for pathology review to confirm eligibility.
- Obtain a Screening ID (format: XXXX-3026-YYYY) from the GOG Partners' IRT System (https://partners.gog.org).
- Print IRT Screening Confirmation
- Send H&E stained slide (labeled with Screening ID) along with a completed copy of the Digital Pathology Screening Form (Appendix E) and printout of the IRT Screening Confirmation to:

GOG 3026 Pathology Review Biopathology Center Nationwide Children's Hospital [name]

[name] [contact]

- Receive results of pathology review via email to registrar patient.
- If pathology review results indicate patient is eligible (and all other eligibility criteria are met), return to the GOG Partners' IRT System to complete patient registration. Once completed, proceed to Rave for patient data entry.
- If pathology review results indicate patient is not eligible, no further action is required in the GOG Partners' IRT System.

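### Renal eligibility is stated two incompatible ways: criterion 11f and the synopsis admit women whom Section 4.7.1.6 says are excluded

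*Combined protocol and SAP*

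**What the plan says.** Section 3.1, item 11, sets laboratory entry requirements: "Patient has adequate bone marrow and organ function as defined by the following laboratory values at screening". Its renal line, 11f, reads "Serum creatinine <1.5 mg/dL or creatinine clearance ≥50 mL/min". The synopsis carries the same line. The two limits are joined by 'or', so meeting either is enough.

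Section 4.7.1.6, under renal impairment, first says "Insufficient data are available to provide a dosage recommendation for ribociclib in patients with renal impairment". It then says "Patients with baseline renal impairment are excluded from the study (serum creatinine > ULN or creatinine clearance <50 mL/min". Here too the limits are joined by 'or', but as an exclusion, so failing either is enough to keep a patient out. The same paragraph adds an on-treatment rule: "Patients who experience renal impairment of grade 2 or higher during the treatment period should discontinue treatment".

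The starting dose does not depend on renal function. Section 4.1 says "Ribociclib will be administered as a flat-fixed dose of 600 mg daily, and not by body weight or body surface area". Registration under Section 6.1 proceeds on this condition: "If pathology review results indicate patient is eligible (and all other eligibility criteria are met". The exclusion list in Section 3.2 has no renal item, and the documents do not say which section prevails if two disagree.

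**The concern.** Two current sections give opposite answers for the same woman. A site working from Section 3.1 would register her and start her at 600 mg. The protocol states elsewhere that she is not in the trial, and states just before that exclusion that there is no basis for recommending a dose in renal impairment. Another site, reading 4.7.1.6, would turn her away.

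At stake are consistent enrolment across the planned 25 centers and a clear position on whether the full dose is acceptable at low clearance. Three provisions limit the consequence without settling baseline status:

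- Exclusion 6 rests on investigator judgment, concerns severe or uncontrolled conditions, and sets no renal threshold.
- The renal DLT (creatinine of grade 3 or higher) acts only after dosing.
- The on-treatment stop in 4.7.1.6 also acts only after dosing.

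**Working it through.** The plan has no figure of its own to reproduce here. The check is a comparison of two rules, followed by an illustration.

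**1. The rules side by side**

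- 11f and synopsis: admit if creatinine <1.5 mg/dL OR clearance ≥50 mL/min.
- 4.7.1.6: exclude if creatinine >ULN OR clearance <50 mL/min.

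The documents give no ULN. The table assumes it is below 1.5 mg/dL.

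| Creatinine (mg/dL) | Clearance (mL/min) | 11f | 4.7.1.6 | Result |
|---|---|---|---|---|
| ≤ULN | ≥50 | admits | does not exclude | agree |
| ≤ULN | <50 | admits | excludes | conflict |
| >ULN and <1.5 | ≥50 | admits | excludes | conflict |
| >ULN and <1.5 | <50 | admits | excludes | conflict |
| ≥1.5 | ≥50 | admits | excludes | conflict |
| ≥1.5 | <50 | does not admit | excludes | agree |

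The conflict for creatinine <1.5 with clearance <50 does not depend on the ULN, because the clearance limb of 4.7.1.6 excludes by itself. The conflicts at clearance ≥50 do depend on it.

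**2. Who could fall in the clearance conflict**

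The documents name no clearance formula. As an illustration only, assume the usual one for women:

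clearance = (140 − age) × kg × 0.85 / (72 × creatinine)

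Setting clearance to 50 gives the creatinine above which clearance falls below 50:

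creatinine = (140 − age) × kg × 0.85 / 3600

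For age 60 and 60 kg this is 80 × 60 × 0.85 / 3600 = 1.13 mg/dL. She is discordant on clearance from there up to 1.5 mg/dL. Over assumed ages and weights:

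| Weight | Age 50 | Age 60 | Age 70 |
|---|---|---|---|
| 50 kg | 1.06 | 0.94 | 0.83 |
| 60 kg | 1.27 | 1.13 | 0.99 |
| 70 kg | 1.49 | 1.32 | 1.16 |
| 80 kg | 1.70 (no window) | 1.51 (no window) | 1.32 |

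At 70 kg and age 50 there is essentially no window. Just under the creatinine limit, at 1.49 mg/dL, 11f admits clearances of about 43, 38 and 33 mL/min at 60 kg (ages 50, 60, 70), and about 50, 44 and 39 at 70 kg. The window is widest in small, older women and closes in heavier, younger ones.

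**3. Would changing 'or' to 'and' in 11f be enough?**

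No. If 4.7.1.6 stays as it is, a woman is still discordant when her creatinine lies above ULN but below the smaller of 1.5 and the table value. For age 60 and assumed ULNs of 0.9, 1.1 and 1.3 mg/dL:

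- 60 kg: 0.9–1.13, 1.1–1.13, none.
- 70 kg: 0.9–1.32, 1.1–1.32, 1.3–1.32.
- 80 kg: 0.9–1.5, 1.1–1.5, 1.3–1.5.

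The creatinine limit has to be aligned as well.

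**4. The two-stage design**

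Averaging exact binomial probabilities over the permitted accruals (19–26, then 44–51) with the Section 11.3 boundaries gives early stopping 0.636 and type I error 0.099 at a 10% response rate, and power 0.900 at 25%. These match the stated 64%, 10% and 90%. Renal status does not enter the calculation.

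**The case against.** The best defense is that Section 3.1 is the operative list. It is headed as patient selection, agrees word for word with the synopsis on this item, and is what a site would naturally use at registration. The sentence in 4.7.1.6 sits in dose-modification text that shows signs of incomplete editing: Section 4.7.1.7 retains an unfilled bracketed placeholder for co-treatment, and the heading of 4.7.1.4 cites CTCAE v4.03 although the trial grades by v5.0. So 4.7.1.6 may be the stale text. That stands as a possibility, and the fix must allow for it. It does not remove the conflict, because the sentence declares a study exclusion and nothing subordinates it to Section 3.1.

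A reader might infer that 11f is the mistake and that 600 mg is unsafe for these women. The documents do not show this. They report no harm in this group, and 4.7.1.6 also says data are insufficient for a dosage recommendation in the elderly, who are enrolled at the same dose with caution. Lack of data is a reason to choose a rule deliberately; it is not evidence of harm.

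A reader might also infer a threat to the primary analysis, since Section 11.5 drops ineligible patients. At a boundary, one reclassified non-responder could matter: 3 of 26 stops the trial at stage 1, whereas 3 of 25 meets the response threshold to continue; 7 of 46 rejects the regimen, whereas 7 of 45 does not. These are edge cases. Ineligibility is most naturally read against Section 3, and no effect on the design's error rates has been shown.

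**Conclusion.** The contradiction is real and follows from the text alone for creatinine below 1.5 mg/dL with clearance below 50 mL/min. The further conflict for creatinine above ULN rests on the assumption that the ULN is below 1.5 mg/dL. The creatinine windows rest on the assumed formula, ages and weights. Section 1.1 associates this disease with younger age at diagnosis, which points toward narrower windows, but the documents give no age, weight or renal distribution for enrolled patients. The number affected is unknown and may be zero.

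The documents do not establish which rule was intended. The point is an eligibility and dosing inconsistency that should be corrected; it does not undermine the two-stage design.

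**What to change.** Put one identical renal rule, with one creatinine limit, in the synopsis, Section 3.1 item 11f and Section 4.7.1.6.

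- **Safer alignment.** Require clearance ≥50 mL/min of every patient, together with a single creatinine limit (ULN or 1.5 mg/dL, the sponsor's choice). Clearance can be calculated by each site's usual method. This is preferred because 4.7.1.6 both excludes these women and says dosing data are insufficient.
- **If 11f was intended.** Correct the exclusion sentence in 4.7.1.6 to match it, and confirm that 600 mg is acceptable with clearance <50 mL/min.

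Section 11.5 needs no change once the rule is aligned.

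The cost is a wording amendment. No new laboratory test is needed, since Section 6.1 already lists "Labs: CMP, CPK, CBC with differential (diff), Uric acid, Urinalysis" at screening; if the site's method uses body weight, it can be taken at the screening physical exam. Under the safer alignment, an unknown number of women with clearance <50 mL/min, or with creatinine above the chosen limit, become ineligible. Choosing ULN costs more: under the assumptions above, an 80 kg woman aged 60 with creatinine between ULN and 1.5 mg/dL has clearance above 50, is eligible under 11f today, and would be lost.

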4.7.1.7 Concomitant Medications

Permitted concomitant therapy

Medications required to treat AEs, manage cancer symptoms, concurrent diseases and supportive care agents, such as pain medications, anti-emetics and anti-diarrheal are allowed. Please consult the list of prohibited medications and the list of use with caution medications for further guidance.

The patient must be told to notify the investigational site about any new medications she takes after the start of the study treatment. All medications (other than study drugs) and significant non-drug therapies (including vitamins, herbal medications, physical therapy and blood transfusions) administered within 30 days of study entry and during the study must be listed on the Concomitant medications/Significant nondrug therapies section of the patient record.

Bisphosphonates and denosumab

Adjuvant bisphosphonate/denosumab therapy is allowed per local and ASCO guidelines. Bisphosphonates and denosumab are permitted for the treatment of osteoporosis and prevention of skeletal related events for patients with bone metastases. Chronic concomitant bisphosphonate/denosumab therapy for the prevention of bone metastasis is not permitted.

Hematopoietic growth factors

Hematopoietic growth factors may be used according to ASCO guidelines.

Selective radiotherapy

Selective radiotherapy is permitted. It should not be delivered to a target lesion Cumulative courses of RT should not encompass > 25% of irradiated bone marrow. No dose modification of study treatment is needed during selective radiotherapy.

Permitted concomitant therapy requiring caution

Medications to be used with caution during ribociclib and [If applicable: and co-treatment] in this study are listed below (see Table 2). This list is not comprehensive and is only meant to be used as a guide. These medications should be excluded from patient use if possible. If they must be given, then use with caution and consider a ribociclib interruption if the concomitant medication is only needed for a short time.

- Moderate inhibitors or inducers of CYP3A4/5
- Sensitive substrates of CYP3A4/5 that do not have narrow therapeutic index
- Strong inhibitors of BSEP
- Sensitive substrates of the renal transporters, MATE1 and OCT2
- Sensitive substrates of BCRP
- Medications that carry a possible risk for QT prolongation

Corticosteroids

Chronic dosing of corticosteroids such as dexamethasone and prednisone is known to lead to induction of CYP3A enzymes, thereby potentially increasing the risk of reducing ribociclib drug exposure to subtherapeutic levels. Systemic corticosteroid treatment should not be given during the study, except for:

- Topical applications (e.g., rash), inhaled sprays (e.g., obstructive airways diseases), eye drops or local injections (e.g., intra-articular);
- A short duration (< 5 days) of systemic corticosteroids ≤ to the anti-inflammatory potency of
 4 mg dexamethasone (e.g. for chronic obstructive pulmonary disease, or as an antiemetic)

Prohibited concomitant therapy

The following medications are prohibited during study treatment in the study (see Table 1). This list is not comprehensive and is only meant to be used as a guide.

- Strong inhibitors or inducers of CYP3A4/5
- Substrates of CYP3A4/5 with a narrow therapeutic index
- Medications that carry a known risk for QT prolongation
- Other investigational and antineoplastic therapies not part of the study
- Herbal medications/preparations, dietary supplements (except for vitamins) including, but not limited to: St. John's wort, Kava, ephedra (ma huang), gingko biloba, dehydroepiandrosterone (DHEA), yohimbe, saw palmetto, black cohosh and ginseng. Patients should stop using all herbal medications and dietary supplements at least 7 days prior to first dose of study treatment.

Drugs with QT prolongation

As far as possible, avoid co-administration of QT prolonging drugs or any other drugs with the potential to increase the risk of drug-related QT prolongation (e.g., via a potential DDI that increases the exposure of ribociclib or the exposure of the QT prolonging drug). A definitive list of drugs with a known risk, possible risk, or conditional risk of QT prolongation and/or Torsades de Pointes (TdP) is available online at www.qtdrug.org.

Medications with a known risk for QT prolongation are prohibited during study treatment.

For complete information, refer to the ribociclib (LEE011) Investigator's Brochure and other drug package insert. See **Appendix C** for information on possible interactions with other drugs.

4.7.2 Letrozole - Dose Modification Guidelines

Toxicity Site	Observation	Management
Bone Effects	Use of Letrozole may cause decreases in bone mineral density (BMD)	Consideration should be given to monitoring BMD
Grade 3-4 hypercholesterolemia	Hypercholesterolemia was reported in 52.3% of letrozole patients and 28.6% of tamoxifen patients.	Consideration should be given to monitoring serum cholesterol.
Subjects with cirrhosis and severe hepatic impairment		Reduce dose to 2.5mg every other day

5.0 PATIENT ENTRY/RANDOMIZATION PROCEDURE

Regulatory Requirements: Please see the Regulatory Manual for site requirements prior to screening and enrollment of patient.

Patient Entry and Registration: The GOG Partners' IRT System (https://partners.gog.org) will be used for patient registration following the completion of the Pathology Screening (see Section 6.1 for instruction for obtaining a Screening ID).

6.0 Study Parameters

6.1 Pre-Treatment Evaluations (Screening)

The following must be collected/ performed within 28 days prior to Cycle 1, day 1 of treatment. Clinical and laboratory evaluations performed as part of routine standard of care do not need to be repeated if performed within the appropriate window.

- Voluntary, written, dated, and signed informed consent must be obtained before any study specific procedures are performed (with the exception of certain imaging assessments if meeting the criteria defined in this section).
- Radiographic tumor assessments that were performed before the signing of the informed consent form as routine procedures (but within 28 days prior to study enrollment) do not need to be repeated and may be used as baseline assessments, as long as:
 - The tests were performed per the method requirements outlined in the Tumor Assessment Requirement Flowchart, the Efficacy Assessments sections.
 - Appropriate documentation indicating that these radiographic tumor assessments were performed as standard of care is available in the patient's source notes
- Complete medical history and disease treatment history.
- UPT in WOCBP
- ECOG PS
- Baseline AE assessment
- Physical exam with vital signs
- Labs: CMP, CPK, CBC with differential (diff), Uric acid, Urinalysis
- ECG
- Tumor assessment CT chest, abdomen, and pelvis, or MRI
- Concomitant medication
- CA-125
- Lipid panel (total cholesterol, HDL, LDL, triglycerides) fasting preferred
- Coagulation (PT and INR)
- Submission of an H&E stained slide for pathology review to confirm eligibility.
- Obtain a Screening ID (format: XXXX-3026-YYYY) from the GOG Partners' IRT System (https://partners.gog.org).
- Print IRT Screening Confirmation
- Send H&E stained slide (labeled with Screening ID) along with a completed copy of the Digital Pathology Screening Form (Appendix E) and printout of the IRT Screening Confirmation to:

GOG 3026 Pathology Review Biopathology Center Nationwide Children's Hospital [name]

[name] [contact]

- Receive results of pathology review via email to registrar patient.
- If pathology review results indicate patient is eligible (and all other eligibility criteria are met), return to the GOG Partners' IRT System to complete patient registration. Once completed, proceed to Rave for patient data entry.
- If pathology review results indicate patient is not eligible, no further action is required in the GOG Partners' IRT System.

Special Note Regarding the Safety Lead-In

For the Safety Lead-in portion, the assigned Screening ID also serves as a slot reservation. These reservations are not transferrable to other patients, and if the patient is not enrolled within the required timeframe, the reservation is cancelled and the slot is then made available to other patients and sites. If all slots for the lead-in are reserved, including existing enrollments, patients can be added to a waiting list. Patients on the waiting list can begin the pathology screening process noted above, but may be unable to be enrolled during the Safety Lead-in if accrual is met in the interim.

To mitigate the risk of over-accrual, the number of active screening patients will be limited in that the sum of patients enrolled and active screening patients cannot exceed the total for phase or study accrual. If a patient in screening is found to not be eligible, or has elected to seek other treatment, this information should be reported in the IRT system as soon as possible. Any "stale" screening patient records will be marked as inactive after 30 days to help in the monitoring of accrual.

Treatment should be initiated within 7 days of registration.

Please refer to the Regulatory Manual for more information regarding the safety lead-in.

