- 12. Patient who has received radiotherapy ≤4 weeks or limited field radiation for palliation ≤2 weeks prior to starting study drug, and who has not recovered to grade 1 or better from related side effects of such therapy (exceptions include alopecia) and/or in whom ≥25% of the bone marrow (Ellis, 1961) was irradiated.
- 13. Patient has had major surgery within 14 days prior to starting study drug or has not recovered from major side effects (tumor biopsy is not considered as major surgery).
- 14. Patient with a Child-Pugh score B or C.
- 15. Patients who are pregnant or breastfeeding
- 16. Women of child-bearing potential, defined as all women physiologically capable of becoming pregnant, unless they are using highly effective methods of contraception throughout the study and for 3 weeks after study drug discontinuation. Highly effective contraception methods include:
 - Total abstinence when this is in line with the preferred and usual lifestyle of the patient. Periodic abstinence (e.g., calendar, ovulation, symptothermal, post-ovulation methods) and withdrawal are not acceptable methods of contraception
 - Female sterilization (have had surgical bilateral oophorectomy with or without
 hysterectomy), total hysterectomy, or tubal ligation at least six weeks before taking
 study treatment. In case of oophorectomy alone, only when the reproductive status
 of the woman has been confirmed by follow up hormone level assessment

Women are considered post-menopausal and not of child bearing potential if they have had 12 months of natural (spontaneous) amenorrhea with an appropriate clinical profile (e.g. age appropriate, history of vasomotor symptoms) or have had surgical bilateral oophorectomy (with or without hysterectomy) or tubal ligation at least six weeks ago. In the case of oophorectomy alone, only when the reproductive status of the woman has been confirmed by follow up hormone level assessment is she considered not of child bearing potential.

- 17. Current use of food or drugs known to be potent CYP3A4 inhibitors, drugs known to be potent CYP3A4 inducers, and drugs that are known to prolong the QT interval (see Appendix C for Prohibited Concomittant Medications).
- 18. Patients whose tumors contain both low-grade serous carcinoma (LGSC) and high-grade serous carcinoma (HGSC).
- 19. Patients with history of haemopoietic stem cell or bone marrow transplant.

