8.1.2 Methods for Evaluation of Measurable Disease

All measurements should be taken and recorded in metric notation using a ruler or calipers. All baseline evaluations should be performed as closely as possible to the beginning of treatment and never more than 4 weeks before the beginning of the treatment.

The same method of assessment and the same technique should be used to characterize each identified and reported lesion at baseline and during follow-up. Imaging-based evaluation is preferred to evaluation by clinical examination unless the lesion(s) being followed cannot be imaged but are assessable by clinical exam.

Clinical lesions Clinical lesions will only be considered measurable when they are superficial (e.g., skin nodules and palpable lymph nodes) and ≥10 mm diameter as assessed using calipers (e.g., skin nodules). In the case of skin lesions, documentation by color photography, including a ruler to estimate the size of the lesion, is recommended.

Chest x-ray: Lesions on chest x-ray are acceptable as measurable lesions when they are clearly defined and surrounded by aerated lung. However, CT is preferable.

Conventional CT and MRI: This guideline has defined measurability of lesions on CT scan based on the assumption that CT slice thickness is 5 mm or less. If CT scans have slice thickness greater than 5 mm, the minimum size for a measurable lesion should be twice the slice thickness. MRI is also acceptable in certain situations (e.g. for body scans), but NOT lung.

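### Nothing requires the RECIST baseline scan to follow the last prior anticancer treatment, so shrinkage from that treatment can be counted as response

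*Combined protocol and SAP*

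**What the plan says.** **Age of the scan.** The lead-in to Section 6.1 sets the screening window: "The following must be collected/ performed within 28 days prior to Cycle 1, day 1 of treatment". Section 6.2 and footnote a of the Section 6.5 schedule use the same anchor (Cycle 1 Day 1 or first dose). Section 8.1.2 wants baseline evaluations close to the start of treatment and "never more than 4 weeks before the beginning of the treatment". The bullet in Section 6.1 on routine pre-consent scans counts from enrollment instead: "but within 28 days prior to study enrollment) do not need to be repeated and may be used as baseline assessments". It adds two conditions, on imaging method and on source documentation. Neither concerns the order of scan and prior treatment.

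**Prior treatment.** Section 3.2, item 13, excludes a patient if "Patient has had major surgery within 14 days prior to starting study drug or has not recovered from major side effects". Item 12 sets 4 weeks for radiotherapy in general, but a shorter limit for "limited field radiation for palliation ≤2 weeks prior to starting study drug". Section 3.1 allows any number of prior therapies. For standard chemotherapy and targeted drugs its only timing-related condition is item 10: "Resolution of all acute toxic effects of prior therapy or surgical procedures to National Cancer Institute (NCI) CTCAE Grade ≤ 1".

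**Response.** Section 8.1.3.1 defines partial response as a fall of at least 30% from the baseline sum of diameters. Section 8.1.3.4 requires confirmation at least 4 weeks later.

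**The concern.** The scan window is longer than some of the prior-treatment windows, and no rule sets the order of the two events. A site can scan on day -28, have the patient undergo surgery or finish palliative radiotherapy on day -15, start study drug, and meet the timing rules throughout. If a target lesion was removed or shrunk in between, the first on-study scan already shows a fall that owes nothing to ribociclib + letrozole.

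Confirmation at 4 weeks does not screen this out, because tumor removed or reduced before dosing can still be smaller at the next scan. Section 4.7.1.7 keeps radiotherapy away from target lesions, and Appendix C bars other anticancer therapy, but both apply during study treatment and not between scan and first dose. Section 8.1.1 says the conditions for using lesions in a previously irradiated area must be defined in the protocol, and they are not.

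There is no control arm in which the same error would also appear. Shrinkage carried over from earlier treatment can only add responders.

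**Working it through.** **1. Length of the gap.** Latest permitted scan age: 28 days before first dose. Surgery and limited-field palliative radiotherapy: excluded within 14 days. Gap = 28 − 14 = 14 days, approximately. For standard chemotherapy or targeted therapy no interval is stated, so most or all of the 28 days is open, limited only by recovery to grade 1 or better.

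**2. Where the gap is closed.** Aromatase inhibitors given for other indications (6 months), tamoxifen or toremifene (5 half-lives), investigational drugs (30 days or 5 half-lives, whichever is longer), CNS disease (4 weeks from prior therapy) and radiotherapy other than limited-field palliation (4 weeks) have their own windows. The radiotherapy limits are joined by an and to lack of recovery ("limited field radiation for palliation ≤2 weeks prior to starting study drug, and who has not recovered to grade 1 or better"), so read literally a recovered patient could have been irradiated later still. The point does not rely on that reading.

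**3. Can a patient with a treated target lesion still enter and count?** Measurable disease is required, but up to five target lesions are allowed (Section 8.1.1). Assume k target lesions of equal diameter, one of them removed after the scan. The sum falls by 1/k: 50% for k = 2, 33% for k = 3, 25% for k = 4, 20% for k = 5. With two or three lesions the 30% threshold is passed with no drug effect, while measurable disease remains. With four or five, one lesion is not enough on its own.

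**4. The plan's own operating characteristics.** Inputs from Section 11.3: null rate 10%, alternative 25%; stage 1 of 19-26 patients, continue if more than 2 of 19-25 or more than 3 of 26 respond; cumulative 44-51 patients, positive if more than 6 of 44-45 or more than 7 of 46-51 respond. Exact binomial calculation, averaged with equal weight over the 8 × 8 = 64 size pairs:

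| Quantity | Stated | Recomputed |
|---|---|---|
| Early termination at 10% | 64% | 63.6% |
| Type I error | 10% | 9.9% |
| Power at 25% | 90% | 90.0% |

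The plan's figures reproduce.

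**5. One carry-over responder, at target size 23/48 and a true rate of 10%.**

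- None: P(stop) = P(Bin(23, 0.1) ≤ 2) = 0.0886 + 0.2265 + 0.2768 = 0.592, so P(continue) = 0.408. P(positive) = Σ over x ≥ 3 of P(Bin(23, 0.1) = x) · P(Bin(25, 0.1) ≥ 8 − x) = 0.0905.
- One, fixed as a responder in stage 1: the other 22 need at least 2 responses to continue. P(stop) = 0.9²² + 22 · 0.1 · 0.9²¹ = 0.0985 + 0.2407 = 0.339, so P(continue) = 0.661. P(positive) = Σ over x ≥ 2 of P(Bin(22, 0.1) = x) · P(Bin(25, 0.1) ≥ 7 − x) = 0.177.

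Averaged over the permitted sizes:

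| Carry-over responders | False-positive probability |
|---|---|
| None | 9.9% |
| One in stage 1 | 19.4% |
| One in stage 2 | 16.3% |
| One in each stage | 30.5% |

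**6. Allowing for the event not happening.** Let q be the chance that the trial has one such stage-1 patient and otherwise none (an assumption; the documents give nothing). At 23/48 the overall type I error is 0.0905 + q · (0.1768 − 0.0905): 9.5% for q = 5%, 9.9% for q = 10%, 10.8% for q = 20%.

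**The case against.** The strongest reply is that the event is rare and largely guarded against. Section 1.1 calls the disease relatively chemoresistant, and Section 1.3 reports a 9% response rate to hormonal therapy, so a late 30% fall from a previous drug should be uncommon. Section 1.3 also says that hormonal therapy is increasingly replacing chemotherapy, and aromatase inhibitors and tamoxifen have their own washouts. Treatment history is collected at screening, and a patient whose measurable disease had all been removed would raise an eligibility question. All this stands as a limit on frequency. None of it sets the order of scan and treatment, and it bears least on surgery and palliative radiotherapy.

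The rise to 17.7% is conditional on one spurious responder with certainty. That also stands: step 6 shows that the unconditional effect is small if such patients are unlikely.

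A reader might go further and infer that the baseline scan may be 35 days old, by adding the 28 days before enrollment to the note in Section 6.1 that "Treatment should be initiated within 7 days of registration", which would widen the gap to about 21 days. The documents taken together do not support this. The lead-in to Section 6.1, Section 6.2, the schedule footnote and Section 8.1.2 all cap the scan at 28 days before treatment, and the 7-day sentence sits under the safety lead-in note. Nor does an old scan by itself inflate response: if untreated tumor grows before dosing, an earlier and smaller baseline makes a 30% fall harder to reach. Only treatment between scan and first dose pushes the result upward.

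**Conclusion.** The point holds in a limited form. As written, the protocol allows major surgery, limited-field palliative radiotherapy or standard systemic therapy to fall between the baseline scan and first dose, over a gap of about 14 days (longer for systemic therapy), and the resulting shrinkage can count as a confirmed response. It does not extend to the agents and settings that have their own longer window.

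The size is a sensitivity figure and not an estimate of trial-level inflation. Given exactly one such responder in stage 1 and a true rate of 10%, the false-positive probability goes from 9.0% to 17.7% at 23/48, or from 9.9% to 19.4% on average over the permitted sizes. The frequency is unknown. The two-stage design itself is sound and its stated figures reproduce. The mismatch between the enrollment and Cycle 1 Day 1 anchors is a matter of consistency and not a source of upward bias. This is a cheap improvement.

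**What to change.** Add one condition to Section 6.1 and repeat it in Section 8.1.2: a scan may serve as the RECIST baseline only if it was obtained after the patient's most recent anticancer surgery, radiotherapy or systemic therapy; otherwise it must be repeated before first dose.

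Separately, bring the enrollment anchor in the pre-consent scan bullet of Section 6.1 into line with the Cycle 1 Day 1 anchor used in that section's lead-in, Section 6.2, the Section 6.5 footnote and Section 8.1.2.

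The cost is a short amendment and an occasional repeat or later-timed scan. Sample size, decision boundaries, eligibility and all treatment and washout rules stay as they are.
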